Unsolicited adverse event:	Any AE reported in addition to those solicited during the clinical study. Also, any 'solicited' symptom with onset outside the specified period of follow-up for solicited symptoms will be reported as an unsolicited adverse event.

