12.5.3.1. Other Solicited Adverse Events

The use of analgesics/antipyretics for either prophylactic or treatment purposes will be recorded as other solicited events in the Subject Diary (eDiary) and subsequently recorded onto the eCRFs and subject medical records.

The study staff must review the data entered into the Subject Diary as described in Section [12.5.8](#).

Note: Any solicited adverse event that meets any of the following criteria must be entered into subjects' source document (see Section [12.5.8](#)) and also as an adverse event on the Adverse Event eCRF:

- Solicited local or systemic adverse event that leads to a visit to a healthcare provider (medically attended adverse event, see Section [12.5.8.3.3](#)).
- Solicited local or systemic adverse event leading to the subject withdrawing from the study or the subject being withdrawn from the study by the investigator (adverse event leading to withdrawal).
- Solicited local or systemic adverse event that otherwise meets the definition of a serious adverse event (see Section [12.5.2](#)).

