- The subject/subject's parent(s)/LAR(s) will select an alarm time that suits their daily routines whilst ensuring compliance with protocol requirements.

Subject eDiary instructions must ensure that the subject/subject's parent(s)/LAR(s) understands the following:

- Timely completion of the Subject eDiary on a daily basis is a critical component to study participation.
- The Subject eDiary will allow certain time windows for completion of each day's observations.
- The Subject eDiary employs the use of audio-visual alarms to ensure timely completion of data entry.
- The trained and assigned user of the Subject eDiary must not share access codes with anyone.
- A helpdesk will be provisioned for users of Subject eDiary in case of technical issues, though it must be stressed that the Helpdesk is not a replacement for normal medical care and no medical issues can be discussed with the agents.
- The Subject eDiary itself must never be considered a substitute for direct medical care and any concerns must be communicated to site staff as soon as possible.
 - The subject/parent(s)/LAR(s) will be contacted by the site staff on Days 15, 75, 105, 181, 271, 361, and 451 (**or Days 15, 75, 105, 181, and 271 for subjects who have not reached Day 271 at the time this amendment takes effect** via a scripted safety follow-up phone call. At, or in advance of each phone call the site will review the eDiary web-portal for responses entered by the subject/subject's parent/LARs in order to solicit additional information during the phone call e.g. related to unsolicited adverse events, concomitant vaccinations/medication and medically attended events (**Amended 11 October 2022**).
- Any new safety information reported during the safety follow-up phone call or site visits (including a solicited adverse event) cannot be entered into the Subject eDiary. Such information must be described in the source documents as a verbally-reported event. Any adverse event reported in this fashion must be described as an unsolicited adverse event and therefore entered into the eCRF.

- The subject and/or subject's parent(s)/LAR(s) will bring the eDiary at each visit. The eDiary will be collected by site staff at Day 121 (Visit 5).

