12.5.8.1. Post-vaccination reminders

Reminder calls or alerts are not intended to be an interview for collection of safety data. If the subject/subject's parent(s)/LAR(s) wishes to describe safety information, this information should only be collected by a healthcare professional at the site, and the safety data described must be written down in the subject's medical chart.

12.5.8.1.1. *Subject Diary Alerts*

The subject/subject's parent(s)/LAR(s) will receive daily reminders via the Subject Diary device's in-built audio-visual alarms to alert the user to complete the diary during the post vaccination period, which is from Day 1 though Day 7, after each vaccination visit.

The Subject Diary system will also allow for regular alerts to be issued via email to site staff indicating where subjects may need to be contacted due to:

- Non-compliance (i.e. failing to enter or transmit diary data),
- Reporting of any severe solicited reactions,
- Subject experienced an unsolicited adverse event that required hospitalization or visit to the emergency room or medically attended events that were of concern to the parents/LAR(s).

Sites must assess these alerts when received and contact subjects as necessary. Please refer to Section 5.3 on the premature withdrawals from the study and Section 12.5.8.3 on the evaluation of Adverse Events for guidance on necessary action in the event of one of these alerts.

12.5.8.2. Time period for detecting and recording adverse events, serious adverse events and pregnancies

All AEs during 30 days following administration of each dose of study vaccines must be recorded into the appropriate section of the eCRF, irrespective of intensity or whether or not they are considered vaccination-related.

Any solicited AE that has not resolved within 30 days post vaccination and is reported during clinic visits or safety follow-up calls will be entered into the subject's eCRF as an unsolicited AE. It will also be included in the subject's source documents at the site by the investigator/site staff as a verbally reported event. It will not be included in the Subject eDiary. These AEs will be analysed as unsolicited AEs (i.e. in the Unsolicited Safety Set).

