5.5.1.3. Analysis of Unsolicited Adverse Events

All safety analyses will be performed using the Exposed set.

This analysis applies to all AEs occurring during the study, judged either as probably related, possibly related, or not related to vaccination by the investigator, recorded in AE eCRF, with a start date on or after the date of first vaccination. All AEs starting prior to the first vaccination will only be listed. The original verbatim terms used by investigators to identify AEs in the eCRFs will be mapped to preferred terms using the MedDRA dictionary. The AEs will then be grouped by MedDRA preferred terms into frequency tables according to system organ class.

All reported AEs, as well as AEs judged by the investigator as at least possibly related to study vaccine, will be summarized according to system organ class and preferred term within system organ class. These summaries will be presented by vaccination group and by interval of study observation. When an AE occurs more than once for a subject, the maximal severity and strongest relationship to the group will be counted.

Separate summaries will be produced for the following categories:

- Serious adverse events (SAEs)
- Adverse Events of Special Interest (AESIs) for subjects who received rMenB+OMV NZ

- Adverse events that are possibly or probably related to vaccine.
- Adverse event leading to withdrawal with relationship to COVID-19.
- Adverse events leading to a medically attended visit.

The frequencies and percentages of subjects who reported at least one immediate unsolicited adverse event (i.e., reactions that occurred during the first 30 minutes after any vaccination that have been flagged as immediate in the eCRF and have not been reported in the eDiary) following any study vaccination will be reported by study group.

Data listings of all AEs will be provided by subject. In addition, AEs in the categories above will be provided as listed data.

Between groups assessment

No statistical tests for between-group comparisons will be performed.

- The percentages of subjects with any unsolicited AEs (including all SAEs) during the 30 days (including the day of vaccination) following the first (Visit 1), the second (Visit 3) and the third (Visit 4) vaccination for all groups will be calculated.

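### Some solicited reactions with onset on Days 1-7 enter the primary 30-day percentage for any unsolicited AE, because SAP 5.5.1.3 selects events by the form they are recorded on

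*SAP*

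**What the plan says.** **The endpoint.** SAP 5.5.1.3 plans, after each of the three vaccinations and for all groups: "The percentages of subjects with any unsolicited AEs (including all SAEs) during the 30 days (including the day of vaccination"). SAP section 2 lists this among the primary safety endpoints.

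**The selection rule.** The same SAP section, like protocol 10.3.4, takes AEs "recorded in AE eCRF, with a start date on or after the date of first vaccination". Neither excludes solicited terms that began inside the solicited window.

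**The definitions.** The protocol glossary (12.1.2) treats as unsolicited what is reported beyond the solicited events, and adds that "any 'solicited' symptom with onset outside the specified period of follow-up for solicited symptoms will be reported as an unsolicited adverse event". Protocol 12.5.4 opens by defining an unsolicited AE as one not solicited through the diary and volunteered by the subject or parent.

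**The recording rules.**
- Protocol 12.5.3.1 requires certain solicited AEs to be entered in the source document "and also as an adverse event on the Adverse Event eCRF". The first criterion is: "Solicited local or systemic adverse event that leads to a visit to a healthcare provider". The other two are withdrawal and seriousness.
- Protocol 12.5.8 bars adding to the eDiary anything first told to staff at a call or visit, solicited reactions included. "Any adverse event reported in this fashion must be described as an unsolicited adverse event and therefore entered into the eCRF".
- Protocol 12.5.8.2 enters a solicited AE still unresolved at 30 days, and reported at a visit or call, in the eCRF as unsolicited: "These AEs will be analysed as unsolicited AEs (i.e. in the Unsolicited Safety Set").
- Protocol 8.2.1 keeps the remaining 7-day solicited AEs in the eDiary only.

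**The concern.** The definitions go by what the event is, when it began and whether the diary captured it. The analysis goes by which form holds the record. Where the two disagree, a sore arm or a headache that began on Day 2 can be reported as an unsolicited event. The documents then give no single answer for a primary safety percentage: a programmer following the glossary and one following SAP 5.5.1.3 would produce different tables. The trial asks whether giving the two vaccines together is tolerable, and this percentage is shown by group. A reader would take it to describe events other than expected reactogenicity.

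**Working it through.** **Step 1. Trace each kind of solicited reaction with Day 1-7 onset through the recording and analysis rules.**

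| Reaction | Protocol section | In the eDiary? | Solicited table | 30-day unsolicited percentage |
|---|---|---|---|---|
| Ordinary | 8.2.1 | Yes | Counted | Not counted |
| Non-serious, medically attended or leading to withdrawal | 12.5.3.1 | Yes | Counted | Counted |
| Serious | 12.5.3.1 | Yes | Counted | Counted; belongs there, since the percentage includes SAEs |
| Unresolved at 30 days | 12.5.8.2 | Yes, for the early days | Counted | Counted, if the eCRF start date is the true onset |
| Reported only verbally | 12.5.8 | No | Not counted | Counted |

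The last row follows from SAP 10.1.2.3, under which a solicited AE exists only if a daily recording of grade 1 or more exists. The documents do not say which start date is entered for a reaction unresolved at 30 days.

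**Step 2. Look for a rule that removes these records.**
- SAP 5.5.1.1 covers solicited AEs found in both eCRF and eDiary and gives priority to the investigator's assessment. It stands under the solicited analysis and is silent on the unsolicited table. It cannot apply to a verbal report with no diary entry.
- SAP 10.1.3.12 merges events with the same term and start day, but only for outputs that combine solicited and unsolicited events.
- SAP 5.5.1.3 does leave out eDiary-reported reactions when it counts immediate unsolicited AEs (first 30 minutes). The overlap is recognised there and not handled for the 30-day percentage.

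No such rule is found.

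**Step 3. Illustrate the size.** The documents state no rate for this endpoint, so there is no figure to reproduce. Every rate below is an assumption:
- u = true unsolicited rate, 15% or 30%
- s = share of subjects with any solicited reaction, 90%, 70% or 40%
- q = share of those subjects with at least one such reaction on the AE eCRF, 1%, 5% or 10%

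Assuming independence, the reported rate is 1 - (1 - u)(1 - s × q), and the inflation is (1 - u) × s × q. Example with u = 0.15, q = 0.05: for s = 0.90, 1 - 0.85 × 0.955 = 18.83%; for s = 0.70, 1 - 0.85 × 0.965 = 17.98%; difference 0.85 points.

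| u | q | Reported, s = 90% | s = 70% | s = 40% |
|---|---|---|---|---|
| 15% | 1% | 15.77 | 15.60 | 15.34 |
| 15% | 5% | 18.83 | 17.98 | 16.70 |
| 15% | 10% | 22.65 | 20.95 | 18.40 |
| 30% | 1% | 30.63 | 30.49 | 30.28 |
| 30% | 5% | 33.15 | 32.45 | 31.40 |
| 30% | 10% | 36.30 | 34.90 | 32.80 |

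- Inflation at s = 90%: 0.63 to 7.65 points, or 2.0 to 24.1 of 315 subjects per group.
- Spurious difference: 0 if the arms react equally, 0.14 to 1.70 points for 90% against 70%, 0.35 to 4.25 points for 90% against 40%.
- Half-width of a 95% interval for a difference with 315 per arm, 1.96 × √(2u(1 - u)/315): 5.6 points at u = 15%, 7.2 points at u = 30%.

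Serious reactions are included in q although they belong in the percentage, so these figures slightly overstate the part that is misplaced.

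**The case against.** **The classification is by collection route, on purpose.** Protocol 12.5.4 speaks of what was not solicited by diary and points to 12.5.3.1; 12.5.8 and 12.5.8.2 reclassify expressly; 10.3.4 carries the same rule as the SAP. The glossary does not use the word only. This largely stands for verbal reports, whose reclassification is deliberate. It does not rescue reactions already in the eDiary. They were solicited by diary, so they fall outside the opening definition in 12.5.4, and they are not additional to the solicited events in the glossary's sense. The glossary's extension to late-onset symptoms would also have no purpose if early-onset ones qualified.

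**Serious, medically attended and withdrawal events are named in the endpoint.** For SAEs this stands, and they should stay. The other two categories have summaries of their own and need not also be in the any-unsolicited percentage.

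**It would be visible.** Events are tabulated by preferred term and listed by subject, so misplaced reactions can be spotted. That helps a careful reader but does not correct the headline percentage.

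**Stronger readings that a reader might infer.**
- *All Day 1-7 reactions are counted as unsolicited.* Protocol 8.2.1 rules this out; only the exceptions reach the form.
- *The solicited and unsolicited percentages err in opposite directions.* This is true only of verbal-only reports. The other routes leave the solicited count intact.
- *The co-administration arm will look worse.* No reactogenicity rates are given. All arms receive rMenB+OMV NZ at Visit 3, and the co-administration arm receives placebo at Visit 4, so any difference could vanish or reverse by dose.
- *The obsolete safety set changes the analysis.* SAP Amendment 3 and protocol 10.3.4 both place safety on the Exposed Set, so the reference in 12.5.8.2 is only a stale label.

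**Conclusion.** The point holds in a limited form. Under the documents' own rules, some solicited reactions with Day 1-7 onset enter the primary 30-day unsolicited percentage. The diary-captured ones are counted twice, and the verbal-only ones are counted as unsolicited alone. The inclusion of non-serious diary-captured reactions contradicts both the glossary and the opening of 12.5.4; for verbal-only reports the conflict is with the glossary.

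The size cannot be derived from the documents. The ranges in the working rest wholly on assumed rates and on independence. Even the largest illustrated arm difference, about 4.3 points, lies inside the sampling uncertainty of such a comparison. No between-group safety test is planned and study success rests on immunogenicity alone, so no error rate or success criterion is affected. The matter is worth settling because the percentage is a primary safety result and the repair uses data already collected.

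**What to change.** In SAP 5.5.1.3:
1. Flag AE eCRF records of a solicited term (injection-site pain, erythema, swelling or induration; fever, nausea, fatigue, myalgia, arthralgia, headache) with onset on Days 1-7 after a dose.
2. Extend the duplicate rule of SAP 5.5.1.1 to the unsolicited table: exclude flagged, non-serious records already captured in the eDiary from the any-unsolicited percentage. Keep them in the medically attended and withdrawal summaries.
3. Keep flagged SAEs in the percentage, since both SAP 5.5.1.3 and SAP 10.1.2.4 include SAEs.
4. Show verbally reported solicited-term events with Day 1-7 onset in a separate row, and give the unsolicited percentage with and without them. Do not add them to the solicited tables: SAP 10.1.2.3 requires a daily recording, and protocol 12.5.8 makes the diary the only source for solicited AEs after the first 30 minutes.

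In the protocol, or by a clarifying note in the SAP, reconcile the glossary and 12.5.4 with 12.5.8 and 12.5.8.2, and delete the obsolete Unsolicited Safety Set reference in 12.5.8.2.

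The cost is one derivation flag, one extra row and the wording changes. No new data are needed.

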Important potential risk: Arthritis	This potential risk is based on a signal observed for Bexsero . Attenuated live virus vaccines (rubella) were reported to be associated with joint-related diseases [Tingle, 1986]. Among inactivated vaccines, different manifestations of arthritis following hepatitis B vaccination (psoriatic arthritis, reactive arthritis, etc.) were described [IOM, 2011]. However, no association with meningococcal vaccines has been reported in the literature. One clinical case of juvenile idiopathic arthritis (JIA) possibly related to Bexsero and 6 spontaneous reports considered to have a possible causal relationship have been observed.	Arthritis will be monitored through the AESI collection (see Section 12.5.5.1).

CONFIDENTIAL

205419 (MENB REC 2ND GEN-045 (V72_79))
Protocol Amendment 7 Final

Important Potential/Identified Risk	Data/Rationale for Risk	Mitigation Strategy
Investigational vaccine: MenACWY (Menveo)		
Important Identified risk: Reconstitution errors	Cases describing medication errors due to administration of the MenCWY conjugate liquid component only without reconstitution with the MenA conjugate lyophilized component, or due to administration of the MenA conjugate lyophilized component only after reconstitution with a different solvent, have been reported during the MenACWY clinical development program.	In several sections of the protocol (e.g., Section 7.1. "Description of study vaccines") it is clarified that the 2 vaccine components have to be reconstituted before vaccine injection.
Important potential risk: GBS	GBS has been observed with other vaccines. No cases have been reported during the MenACWY clinical development program.	The potential risk of events of possible autoimmune aetiology that might occur is mentioned in ICF. GBS will be monitored through the pIMDs and SAE collection (see Section 12.5.5.2).
Important potential risk: ADEM	ADEM has been observed with other vaccines. Two serious cases from clinical trials were retrieved from the GSK's global safety database for MenACWY. None of them has provided sufficient evidence of a causal association between ADEM and MenACWY.	The potential risk of events of possible autoimmune aetiology that can occur is mentioned in the ICF. ADEM will be monitored through the pIMD and SAE collection (see Section 12.5.5.2).

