Important potential risk: Thrombocytopenia	Immune thrombocytopenic purpura has been reported in association with several licensed vaccines. One serious case related to MenACWY has been reported during the clinical development program. This case didn't provide sufficient evidence of a causal association between thrombocytopenia and MenACWY vaccine.	Immune thrombocytopenic purpura will be monitored through SAE collection (see Section 12.5.5.2).
Important potential risk: Facial paresis	Facial paresis was recognized as an important potential risk following the results of a sponsored observational study (V59_34OB) which found an imbalance of cases of facial paresis following vaccination with MenACWY, mainly when administered concomitantly with other vaccines. No cases of facial paresis were reported from interventional clinical trials.	Paralysis of the face is mentioned in the list of side effects in the ICF. Facial paresis will be monitored through SAE collection.
Study Procedures		
Risk of blood sampling	Blood sampling is associated with a risk of syncope, dizziness, and infection after or during venipuncture.	Blood samples will be obtained by a trained professional and medical assistance will be available. The potential risk of feeling faint, experiencing mild local pain, bruising, irritation or redness at the site where blood was taken, is mentioned in the ICF. The amount of blood to be taken for sampling will not be harmful to the health of the subject.

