4. OBJECTIVE(S) AND ENDPOINT(S)

Table 6 Study objectives and endpoints (Amended 11 October 2022)

Objectives	Endpoints
Primary	
To assess the safety and tolerability of rMenB+OMV NZ and MenACWY, when administered concomitantly or alone, in healthy subjects 16-18 years of age.	
 • The frequencies and percentages of subjects with solicited local (i.e., injection site pain, erythema, swelling, induration) and systemic (i.e., fever [temperature $\geq 38.0^{\circ}\text{C}/100.4^{\circ}\text{F}$], nausea, fatigue, myalgia, arthralgia, headache) adverse events (AEs) during the 7 days (including the day of vaccination) following the first (Visit 1, Day 1/Month 0), the second (Visit 3, Month 2) and the third (Visit 4, Month 3) vaccination for all groups. • The frequencies and percentages of subjects with any unsolicited AEs (including all SAEs), AEs leading to withdrawal and medically attended AEs during the 30 days (including the day of vaccination) following the first (Visit 1, Day 1/Month 0), the second (Visit 3, Month 2) and the third (Visit 4, Month 3) vaccination for all groups. • The frequencies and percentages of subjects with SAEs, AEs leading to withdrawal, and medically attended AEs, throughout the study period (Day 1/Month 0 to Month 9). • The frequencies and percentages of subjects (who received rMenB+OMV NZ) with AESI throughout the study period (Day 1/Month 0 to Month 9). • Among subjects who are followed for 12 months after their last dose: 
 ○ The frequencies and percentages of subjects with

CONFIDENTIAL

205419 (MENB REC 2ND GEN-045 (V72_79))

Protocol Amendment 7 Final

Objectives	Endpoints
	
SAEs, AEs leading to withdrawal, between SFU 5 (Month 9) and SFU 7 (Month 15).
 
The frequencies and percentages of subjects (who received rMenB+OMV NZ) with AESI between SFU 5 (Month 9) and SFU 7 (Month 15).

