7.2.2.2.1. Study group and treatment number allocation

The target will be to enroll approximately 945 eligible subjects who will be randomly assigned to 3 study groups in a 1: 1: 1 ratio (approximately 315 subjects in each group).

Subjects will be randomized in the source data base for internet randomization system (SBIR) system to one of the 3 parallel treatment arms in a 1:1:1 ratio to receive:

- Group MenB+MenACWY: rMenB+OMV NZ given concomitantly with MenACWY at study Day 1; rMenB+OMV NZ at study Day 61; Placebo at study Day 91.
- Group MenB: rMenB+OMV NZ given concomitantly with Placebo at study Day 1; rMenB+OMV NZ at study Day 61; MenACWY at study Day 91.
- Group MenACWY: MenACWY given concomitantly with Placebo at study Day 1; rMenB+OMV NZ at study Day 61 and at study Day 91.

The Subject ID will be the subject's unique identification number for all eCRFs and associated study documentation that will be used for duration of the study.

Allocation of the subject to a study group at the investigator site will be performed using a randomization system on internet (SBIR). The randomization algorithm will use a minimization procedure accounting for center.

After obtaining the signed/witnessed/thumb printed and dated ICF/IAF from the subject/ subject's parent/ LAR and having checked the eligibility of the subject, the site staff in charge of the vaccine administration will access SBIR. Upon providing the subject identification number, the randomization system will determine the study group and will provide the treatment number to be used for each component.

The number of each administered treatment must be recorded in the eCRF on the Vaccine Administration screen.

When SBIR is not available, please refer to the SBIR user guide or the Study Procedures Manual (SPM) for specific instructions.

If for any reason, after signing the informed consent form (ICF), the subject who is eligible and enrolled fails to be randomized, this is called a randomization failure and the early termination study procedures must be applied. The reason for all randomization failures should be recorded in the Screening and Enrolment Log and in the source document as specified in the Source Documentation Agreement Form (SDA). The information on subjects who are randomization failures should be kept distinct from subjects who are screen failures, as described in section [6.4](#).

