7.7. Contraindications to subsequent vaccine(s) administration

Prior to receipt of additional study vaccination, subjects must be evaluated to confirm that they are eligible for subsequent vaccination. If subjects meet any of the original exclusion criteria or the criteria listed below, they should not receive additional vaccinations. However, these subjects should be encouraged to continue study participation.

- Anaphylaxis following the administration of vaccines
- Pregnancy (see Section 12.5.7.1)
- Any condition that in the judgment of the investigator would make IM injection unsafe.

- Any occurrence of an event listed in the exclusion criteria which must be always re-assessed by the investigator before administration of the second dose of study vaccine.
- Subjects who experience any serious adverse event (SAE) judged to be possibly or probably related to study vaccine or non-study vaccines, including hypersensitivity reactions.
- Subjects who develop any new condition which, in the opinion of the investigator, may pose additional risk to the subject if he/she continues to participate in the study.
- Occurrence of a new AESI or the exacerbation of an existing AESI. Refer to Section [12.5.5](#) for the definition of AESIs.

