
 • Cranial nerve neuropathy, including paralysis and paresis (e.g. Bell's palsy). • Optic neuritis. • Multiple sclerosis. • Transverse myelitis. • Guillain-Barré syndrome, including Miller Fisher syndrome and other variants. • Acute disseminated encephalomyelitis, including site specific variants e.g.: non-infectious encephalitis, encephalomyelitis, myelitis, myeloradiculoneuritis. • Myasthenia gravis, including Lambert-Eaton myasthenic syndrome. • Demyelinating peripheral neuropathies including: 
 – Chronic inflammatory demyelinating polyneuropathy, – Multifocal motor neuropathy – Polyneuropathies associated with monoclonal gammopathy. • Narcolepsy. 	
 • Systemic lupus erythematosus and associated conditions • Systemic scleroderma (Systemic sclerosis), including: 
 – Diffuse Scleroderma – CREST syndrome • Idiopathic inflammatory myopathies, including: 
 – Dermatomyositis – Polymyositis • Anti-synthetase syndrome. • Rheumatoid Arthritis and associated conditions including: 
 – Juvenile Idiopathic Arthritis – Still's disease. • Polymyalgia rheumatica. • Spondyloarthropathies, including: 
 – Ankylosing Spondylitis, – Reactive Arthritis (Reiter's Syndrome), – Undifferentiated Spondyloarthritis, – Psoriatic Arthritis, – Enteropathic arthritis. • Relapsing Polychondritis. • Mixed Connective Tissue disorder. • Gout. 	
 • Psoriasis. • Vitiligo. • Erythema nodosum. • Autoimmune bullous skin diseases (including pemphigus, pemphigoid and dermatitis herpetiformis). • Lichen planus. • Sweet's syndrome. • Localised Scleroderma (Morphea).

CONFIDENTIAL

205419 (MENB REC 2ND GEN-045 (V72_79))
Protocol Amendment 7 Final

Vasculitis	Blood disorders	Others

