- The percentages of subjects with SAEs, AEs leading to withdrawal, and medically attended AEs, throughout the study period (Day 1 /Month 0 to Month 9) will be calculated. Among subjects who are followed for 12 months after their last dose the percentages of subjects with SAEs, AEs leading to withdrawal, and medically attended AEs, between SFU 5/Month 9 and SFU 7/Month 15 will also be calculated.
- The percentages of subjects with AESI throughout the study period (Day 1 /Month 0 to Month 9) will be calculated (for subjects who received rMenB+OMV NZ). Among subjects who are followed for 12 months after their last dose the percentages of subjects with AESI, between SFU 5/Month 9 and SFU 7/Month 15 will also be calculated.

Descriptive summary statistics will be provided by obesity status (i.e., BMI <30kg/m² vs >30.kg/m²).

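### The Day 1 to Month 9 AESI percentage is limited to rMenB+OMV NZ recipients, so Group MenACWY cases recognised before Visit 3 leave its numerator and denominator in that group only

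*SAP*

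**What the plan says.** Protocol Table 6 (Section 4) defines a primary safety endpoint as the frequency and percentage of "subjects (who received rMenB+OMV NZ) with AESI throughout the study period (Day 1/Month 0 to Month 9"). SAP Section 2 repeats it. SAP 5.5.1.3 lists a separate summary of "Adverse Events of Special Interest (AESIs) for subjects who received rMenB+OMV NZ" and, under the between-groups assessment, says the Day 1 to Month 9 AESI percentage "will be calculated (for subjects who received rMenB+OMV NZ").

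The dosing schedule in protocol 7.2.2.2.1 reads "Group MenACWY: MenACWY given concomitantly with Placebo at study Day 1; rMenB+OMV NZ at study Day 61 and at study Day 91". The other two groups receive rMenB+OMV NZ on Day 1.

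Protocol 7.7 lists criteria after which a subject should receive no more study vaccine. One of them is "Occurrence of a new AESI or the exacerbation of an existing AESI". These subjects are encouraged to stay in the study. AESI recording starts at the first study vaccine of any kind (protocol 12.5.8.2 and Table 3).

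**The concern.** Whether a Group MenACWY subject enters the AESI denominator depends on reaching Visit 3 and being dosed, and an AESI is itself a reason not to be dosed. The denominator in that group therefore depends on the outcome. In the other two groups every exposed subject has received rMenB+OMV NZ by the end of Day 1, so the same event on the same day is counted.

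This matters because the AESI definition is wider than rMenB+OMV NZ risks. For MenACWY, the risk assessment in protocol 3.3.1 says "GBS will be monitored through the pIMDs and SAE collection", and treats ADEM the same way. It also lists facial paresis as a potential risk of MenACWY, citing an observational study that found an "imbalance of cases of facial paresis following vaccination with MenACWY, mainly when administered concomitantly with other vaccines". Facial paresis is assigned to SAE collection, but the pIMD list in Table 28 includes "Cranial nerve neuropathy, including paralysis and paresis", so a non-serious case is still an AESI.

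Day 1 to Visit 3 is the only period in which MenACWY with rMenB+OMV NZ can be compared with MenACWY in subjects who have had no rMenB+OMV NZ. The loss falls in that period and only in the comparator, so the concomitant group can look relatively worse on AESIs than it is.

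**Working it through.** **Tracing one event.** Take an AESI diagnosed on Day 40 in each group.

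| Group | First rMenB+OMV NZ | Dosed at Visit 3 under 7.7? | In AESI denominator? | Event counted? |
|---|---|---|---|---|
| MenB+MenACWY | Day 1 | No | Yes | Yes |
| MenB | Day 1 | No | Yes | Yes |
| MenACWY | Day 61 | No | No | No |

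Neither document starts the Group MenACWY window at the first rMenB+OMV NZ dose, and neither specifies an AESI summary on all exposed subjects.

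**Inputs for the size.** The plan gives no AESI rate, so there is no AESI figure to reproduce. The arm size is 315 per group (protocol 10.1.2). As a check, 250 / (1 − 0.20) = 312.5, which agrees with 315 after rounding up. Nominal intervals (protocol Tables 4 and 5) are 60 days from Visit 1 to Visit 3, 30 from Visit 3 to Visit 4 and 180 from Visit 4 to SFU 5, so 60 + 30 + 180 = 270 days.

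**Assumptions.** The hazard is constant and equal across groups, and there is no other attrition. Recognition lags onset by L days, and a case not yet recognised at Visit 3 is still dosed. A lag is plausible because Table 28 diagnoses become AESIs only once definitive (12.5.5.2), and arthritis carries a 6-week duration threshold (12.5.5.1).

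**Share retained.** Onsets in the first 60 − L days are lost, so reported / all-exposed risk ≈ 1 − (60 − L)/270:

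- L = 0: 1 − 60/270 = 0.78
- L = 14: 1 − 46/270 = 0.83
- L = 30: 1 − 30/270 = 0.89
- L = 42: 1 − 18/270 = 0.93

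**Expected counts.** For an assumed nine-month risk p, λ = −ln(1 − p)/270. Expected exclusions are 315 × (1 − exp(−(60 − L)λ)), and the reported percentage is 1 − exp(−(210 + L)λ). The chance of losing at least one subject is 1 − (1 − p)^(315 × (60 − L)/270). The exponent is 70 for L = 0 and 21 for L = 42.

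| Assumed p | Excluded, L = 0 | Reported | P(≥1) | Excluded, L = 42 | Reported | P(≥1) |
|---|---|---|---|---|---|---|
| 0.2% | 0.14 | 0.156% | 13% | 0.04 | 0.187% | 4% |
| 0.5% | 0.35 | 0.389% | 30% | 0.11 | 0.467% | 10% |
| 1% | 0.70 | 0.779% | 51% | 0.21 | 0.934% | 19% |
| 2% | 1.41 | 1.559% | 76% | 0.42 | 1.868% | 35% |

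**Visit window.** Visit 3 may fall 53 to 88 days after Visit 1. With later intervals nominal, the affected share is 53/263 = 20% to 88/298 = 30%. With equal true risk and no lag, the other groups would appear about 1.25 times (53 days), 1.28 times (60 days) or 1.42 times (88 days) as high as Group MenACWY.

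**What one case does.** With three AESIs among 315 in every group, one of them in Group MenACWY before Visit 3, that group reports 2/314 = 0.64% and the others 3/315 = 0.95%.

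**The case against.** The best answer is that this is an rMenB+OMV NZ endpoint by definition. Arthritis, the AESI with its own section, comes from a signal for that vaccine. An event in someone who never received it is properly outside the endpoint, so the shortfall exists only against an all-exposed risk that the plan does not set out to estimate. That stands as far as it goes: a rate among recipients is a coherent summary and should stay. It does not explain a window that opens on Day 1 in every group. In Group MenACWY, an event that starts before any rMenB+OMV NZ counts if it is recognised after the Visit 3 dose and disappears if it is recognised before.

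The second answer is that the events are reported elsewhere. This also stands. An AESI that stops vaccination is an AE leading to withdrawal, which under protocol 12.5.8.3.2 includes vaccine withdrawal. Most confirmed cases would also be medically attended. Both categories are reported for Day 1 to Month 9 without the rMenB+OMV NZ restriction, and the events appear in the system organ class tables by group and interval and in the listings. What is missing is any AESI percentage that includes them. The SAP leaves its table list to a separate document that was not available here, so one may exist there, but the SAP text does not call for it.

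Group MenB receives MenACWY by itself at Visit 4, but after two rMenB+OMV NZ doses and three months later, so it is no substitute comparator.

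The sizes rest on assumption. Protocol 7.7 also bars subjects with a new condition thought to add risk. Some undiagnosed cases would then not be dosed, which moves the result back towards 0.78. Because 7.7 says should not, a subject dosed despite an AESI would be counted.

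Finally, the distortion makes co-administration look worse, not better; no between-group safety tests are planned; and study success rests on immunogenicity alone.

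**Conclusion.** The concern holds, and it is minor. The restricted population, the Visit 3 first dose and the AESI contraindication together give Group MenACWY an outcome-dependent denominator in a primary safety endpoint, and the other two groups are unaffected. Measured against the all-exposed Day 1 to Month 9 risk, the Group MenACWY percentage is too low. The factor 0.78 is the largest expected shortfall at the nominal schedule; recognition lag moves it towards 0.93. In counts this is below one expected subject for assumed risks up to 1%. The mechanism follows from the text. The size depends on assumed rates, a constant and equal hazard and an assumed lag. The consequence is a descriptive comparison that can mislead, not a wrong test or a lost event.

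**What to change.** In SAP 5.5.1.3, add a descriptive AESI summary (including pIMDs) on the whole Exposed Set by group, split into first vaccination to before Visit 3, and Visit 3 onward. Footnote the existing rMenB+OMV NZ recipient table to say that Group MenACWY subjects whose AESI was recognised before Visit 3, and who were therefore not given rMenB+OMV NZ, are in neither its numerator nor its denominator.

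Leave the protocol endpoint, its population and its window as they are. No change to the vaccination rule in protocol 7.7 is proposed.

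A small wording point: protocol 8.2.1 describes AESI collection as being for rMenB+OMV NZ recipients, while Table 3 and 12.5.8.2 record AESIs from the first study vaccination. These should be reconciled.

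The cost is one table and one footnote. No new data are needed, because AESIs are already recorded in all groups from the first dose.
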